1.6.3. Other Secondary Outcomes

Secondary Outcome 7. The proportion of infants in each intervention arm with an atypical NNNS neurobehavioral profile prior to discharge.

Secondary Outcome 8. The lengths of hospital stay for infants in each intervention arm.

Secondary Outcome 9. Assessments of maternal well-being and maternal-infant attachment after discharge in each intervention arm.

Secondary Outcome 10. Assessments of growth in each intervention arm.

Secondary Outcome 11. Assessment of infant wellness after discharge and until 24 months of age in each intervention arm.

Secondary Outcome 12. Assessment of infant development to 24 months of age in each intervention arm.

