In contrast to variations for weaning in clinical practice, randomized trials have used 10% reductions of the stabilizing dose. In a single-site trial that compared methadone to morphine, clinical teams weaned both drugs by 10% reductions of the stabilizing dose with four-hour dosing intervals (15). The most recent, and largest (58 infants in each group), randomized clinical trial of NOWS treatment, performed by Davis et al., was a multi-center trial comparing methadone to morphine (18). In this trial, medical professionals weaned NOWS infants treated with methadone or morphine by 10% of the stabilization dose every 12 to 48 hours with cessation of drug therapy at 20% of the stabilization dose. Administration of methadone alternating with placebo every four hours and morphine every four hours facilitated blinding of nursery personnel to the opioid being used. The trial demonstrated that the length of treatment and hospital stay were shorter with methadone, compared to morphine, and these results may prompt a shift from morphine to methadone as the primary opioid to treat NOWS. There are no randomized trials to inform clinicians of potentially better regimens to wean morphine or methadone.

Common outcomes of clinical trials of NOWS treatment are length of treatment, length of hospital stay, and safety outcomes. Although clinically evident brain injury on a neurological exam is not anticipated among infants with NOWS, there is support for abnormalities of neurobehavior (24). Such information may be important to understand maternal well-being after hospital discharge of a NOWS-treated baby. This is an important domain of NOWS research, and there is a growing recognition that outcomes of NOWS investigations need to broaden to include measures beyond length of treatment and length of hospital stay (7).

The NNNS is a comprehensive evaluation of 12 domains of neurologic and behavioral functioning as well as signs of stress, administered by trained, certified examiners (25). The research community has used the NNNS to study multiple groups of high-risk infants, including those exposed to drugs *in utero* (opioids, cocaine) and prematurity (26). Among 1,248 mother-infant dyads enrolled in the Maternal Lifestyle Study, researchers performed NNNS assessments at one month *after* hospital discharge (27). Researchers identified five mutually exclusive neurobehavioral profiles from the 12 neurobehavioral

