domains by using latent profile analysis. Profile 5 (black line, **Figure 1**) was the most atypical, and it was characterized by exaggerated scores for arousal, excitability, hypertonicity, quality of movement, and stress abstinence, relative to four other distinct profiles. Researchers have associated Profile 5 with early childhood outcomes, including more externalizing behavior problems, internalizing behavior problems, and total behavior problems at age three, as well as lower IQ scores after adjustment for gestational age and socioeconomic status (27). In this protocol, “atypical neurobehavioral profile” refers to Profile 5 in **Figure 1**.

There is a lack of consensus on the effects of prenatal opioid exposure on neurodevelopmental outcomes in early childhood. A recent comprehensive review indicated that there are discrepant findings with respect to the presence or absence of altered neurodevelopment with in-utero exposure (28). This reflects that many studies are small and cannot adjust for potential confounding variables. Potential confounding variables (e.g., prenatal exposures to other substances, nutrition, socio-economic status, medical complications, poor prenatal care) may all impact early childhood development. Few studies have examined neurodevelopment among infants who develop NOWS, and even less among infants who are pharmacologically treated for NOWS. A retrospective chart review of infants born in 2011-2015 and treated for NOWS with morphine, methadone or buprenorphine had lower Bayley Scales of Infant Development III at 23 months compared with normative data for the Bayley Scales (29). Contemporary data on early childhood neurodevelopment of infants with NOWS in the presence or absence of pharmacologic treatment remains a major research gap.

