5.1.5. Analyses of Secondary Outcomes

We will use the same approach described in the primary outcome analysis to compare the number of days of opioid treatment with only infants receiving morphine as the primary pharmacological treatment for NOWS (Secondary Outcome 1). We will use this same approach to compare the number of days of opioid treatment using only infants receiving methadone as the primary pharmacological treatment for NOWS (Secondary Outcome 2).

We will use adjusted logistic regression models to provide an odds ratio (OR) and 95% Confidence Intervals (CI) for binary secondary outcomes measured only once. These outcomes will include:

- the proportion of infants by intervention arms that escalate or resume opioid medication during weaning,
- for the proportion of infants by intervention arms with an atypical neurobehavioral profile (**Profile 5, Figure 1**),
- the proportion of infants who receive an escalation of a second-line or third-line drug to treat NOWS signs from the first weaning dose to cessation of opioid.

Title: Pragmatic, Randomized, Blinded Trial to Shorten Pharmacologic Treatment of Newborns with Neonatal Opioid Withdrawal Syndrome (NOWS)

Sponsor: National Institutes of Health

We will adjust these models for the stratification variable (hospital), covariates of maternal treatment and stabilization dose, and baseline variables that may differ between groups by chance. We define the covariates that we may adjust for earlier in this section in the paragraph on other collected data.

We will analyze the secondary outcome of the total opioid exposure from the first weaning dose to cessation of opioid in a similar manner as the primary outcome. We will use a regression model that will include: a fixed treatment effect (intervention arms) and adjustment for the stratifying variable, covariates of maternal treatment and stabilization dose, and baseline variables that may differ between groups by chance as fixed effects. We will include hospital (site) as a random effect. The primary test of interest will be the F-test of the intervention arm effect, and we will report the treatment difference along with 95% CI.

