4.1 Modeling Process

For the primary outcome (H1), linear mixed model with site as random effect and intervention as a fixed effect will be used.

For safety outcomes, binomial proportions and their corresponding 95% CI by intervention arm for seizure (clinical and EEG), excessive stool output, respiratory disturbances, and feeding intolerance will be reported. Chi-square/Fisher exact tests will be used to compare between the intervention arms. If we end up with a very small number of adverse events and severe adverse events, analysis of these measures will be descriptive only.

For the secondary linear outcomes (H2, H3, H5 & H12d), linear mixed model with site as random effect will be used. For secondary binary outcomes (H4, H6), generalized linear mixed model with site as random effect will be used. For count outcomes (H12a-12c), generalized linear mixed models using either Poisson or negative binomial distribution and site as random effect will be used. Intervention will be included in the models as a fixed effect. Secondary outcome models will be adjusted for breastfeeding status, maternal treatment, and stabilization dose.

Hypotheses H9 – H11 will be analyzed in a similar manner to H2. For the PROMIS model (H10), we will adjust for 1-month after discharge and if mother is the primary care giver as fixed effect covariates.

Hypothesis H8 will be analyzed using latent profile analysis as specified in Liu et al. (2). Model fit indices and likelihood ratio tests will inform the determination for the most-appropriate number of classes.

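### The SAP's latent profile analysis for H8 is not tied to Profile 5, so the protocol's neurobehavioral outcome is not guaranteed to be estimated

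*SAP*

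**What the plan says.** **Protocol.** Section 1.6.3 states Secondary Outcome 7 as "The proportion of infants in each intervention arm with an atypical NNNS neurobehavioral profile prior to discharge". Section 3.3.2 gives its origin in a cited cohort: "Researchers identified five mutually exclusive neurobehavioral profiles from the 12 neurobehavioral" domains, by latent profile analysis. It describes the fifth as the most atypical, with exaggerated arousal, excitability, hypertonicity, quality of movement and stress abstinence. It then says that the term atypical, in this protocol, "refers to Profile 5 in" Figure 1. Section 5.1.5 says "We will use adjusted logistic regression models to provide an odds ratio (OR) and 95% Confidence Intervals (CI) for binary secondary outcomes measured only once", and its list of such outcomes includes an entry "for the proportion of infants by intervention arms with an atypical neurobehavioral profile", again identified as Profile 5.

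**SAP.** Section 2.2.1 (Research Objective 8) and section 6.3 keep the atypical profile as the name of the outcome. The null and alternative hypotheses under Objective 8 are broader: they concern whether behavioral profiles differ between arms. Section 4.1 gives the only method specific to H8, a latent profile analysis following the cited study, and adds "Model fit indices and likelihood ratio tests will inform the determination for the most-appropriate number of classes". The same section names H4 and H6 as the binary secondary outcomes that receive a generalized linear mixed model. H8 is not among them.

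**The concern.** The protocol's endpoint is a yes/no variable whose definition does not depend on trial results. The SAP's procedure returns a set of classes whose number and shape are learned from trial infants. Nothing in the SAP turns those classes back into the protocol's variable.

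Two things are at stake. First, the named secondary outcome may not be estimated: the chosen solution may contain no class resembling Profile 5, and no fallback is given. Second, someone must decide which class is called atypical. The SAP gives no rule and no requirement that this be settled before arms are compared, so the choice could follow the results.

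**Working it through.** The point rests on text. The arithmetic shows only what can be said about its size.

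**1. The two plans side by side**

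| Element | Protocol (3.3.2, 5.1.5) | SAP (2.2.1, 4.1, 6.3) |
|---|---|---|
| Outcome | Profile 5, yes or no | Labelled atypical; Profile 5 not mentioned |
| Number of profiles | Five, from the cited solution | Guided by fit in trial data |
| Which class is atypical | Profile 5, described by five domains | No rule |
| If no such class appears | Cannot arise by definition | No fallback |
| Arm comparison | Adjusted logistic regression, OR and 95% CI | General hypothesis on profiles; H8 not assigned to the binary model |
| Assigning a new infant | No algorithm given | Latent profile analysis, no mapping to Profile 5 |

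Document versions do not explain the gap. The SAP cites protocol version 10, and the log for version 11 lists face-page changes only. The SAP revision history does not mention a change to this outcome.

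**2. Sample size available.** Neither document gives a sample size or a Profile 5 rate for H8. The revised target in SAP 3.4 is used as the planned size. It reproduces: n per arm = 2(1.960 + 0.842)² × 6.2² / 2.0² = 150.9, rounded up to 151, or 302 in total, as stated.

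**3. Size of the model.** With 12 domains, K classes and equal variances, the free parameters are 12K means + 12 variances + (K − 1) class shares. For K = 5 this is 60 + 12 + 4 = 76. That leaves 302/76 = 4.0 infants per parameter, against 1,248/76 = 16.4 in the cited cohort. With class-specific variances the count is 60 + 60 + 4 = 124.

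**4. Would five classes be chosen?** This simulation uses assumed settings: five true classes (30, 25, 20, 15 and 10%), 12 independent indicators, class means drawn with the SD shown (in within-class SDs), BIC selection and n = 302.

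| SD of class means | Five classes selected |
|---|---|
| 0.5 | 0 of 30 |
| 0.7 | 4 of 30 |
| 0.9 | 9 of 25 |
| 1.2 | 24 of 25 |

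**5. Would the atypical class survive anyway?** This is the question that matters for the endpoint. Assumed settings: n = 302, an extreme class of 8% shifted on the five named domains, BIC selection and 25 runs per setting. Recovery means sensitivity and positive predictive value of at least 70%.

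| SD of other class means | Shift of extreme class | Extreme class recovered |
|---|---|---|
| 0.3 | 2.0 SD | 25 of 25 |
| 0.3 | 1.5 SD | 16 of 25 |
| 0.5 | 1.5 SD | 11 of 25 |

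With the other means at SD 0.3, five classes were selected in 0 of 25 runs. Missing the count of five is therefore not the same as losing the atypical class. Both results turn on separation, which the documents do not give.

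**6. Is the fixed outcome analysable?** Take 151 per arm, two-sided 0.05, a normal approximation and an assumed slow-wean Profile 5 rate p that doubles in the other arm. Power is Φ{[p − 1.96√(2p̄(1 − p̄)/151)] / √([p(1 − p) + 2p(1 − 2p)]/151)}, with p̄ = 1.5p. It is 38% for p = 5%, 68% for 10%, 88% for 15% and 97% for 20%. The outcome can be analysed, but the information in it depends strongly on a rate that the documents do not state.

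**The case against.** The strongest reply is that this is incomplete operationalization, not substitution. Profile 5 itself came from latent profile analysis, and the protocol gives no algorithm for placing a new infant in it, so some classification step was always needed. The SAP says that it follows the cited study, and the protocol's description of Profile 5 could guide the labelling. A fresh fit may also suit this cohort better: the source infants were examined one month after discharge, whereas these drug-treated infants are examined before discharge. Finally, SAP 6.4.4 treats all analyses other than the primary as exploratory.

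Much of this stands. It justifies a new profile analysis as a declared choice with rules, and it limits the seriousness of the point. It does not close the gap. Whatever the cited study specifies, the SAP's next sentence reopens the number of classes, and the SAP does not adopt the protocol's description as its labelling rule.

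Three stronger readings are tempting and are not supported:

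- *That H8 has no arm comparison.* SAP 2.2.1 states a between-arm hypothesis, and SAP 6.4.1 has generic language putting intervention arm and site in all models. What is missing is a defined binary H8 outcome and an explicit assignment of it to that model.
- *That the atypical class would usually be merged away at about 300 infants.* Step 5 shows that this depends on assumed separation.
- *That the link between Profile 5 and childhood outcomes is lost.* The documents do not establish that link for a pre-discharge examination under either method.

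**Conclusion.** The concern holds as a conflict between a protocol endpoint and a stated SAP rule. The protocol's Secondary Outcome 7 is not guaranteed to be estimated under SAP 4.1, and the class called atypical could be settled after results are seen. Nothing in the documents indicates that arm assignment would enter the choice of class number. The exposure is mainly in the labelling, which the SAP leaves open.

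No probability can be put on the harm. The simulations range from no recovery to nearly complete recovery as assumed separation changes, and they use BIC where the SAP names fit indices and likelihood ratio tests without a rule for reconciling them. The conclusion rests on the text and does not depend on the simulations. One secondary outcome is affected; the primary result is not. The change should be made because it is cheap and restores a fixed definition.

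**What to change.** Amend the SAP for H8 before arm labels are used:

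1. **Classification.** If the class parameters of the cited solution are available, assign each infant to its five profiles. Otherwise, fit the profile model once on pooled, arm-blind data, with the rule for the number of classes written down beforehand.
2. **Labelling.** Under a new fit, call atypical the class matching the description in Protocol 3.3.2 (exaggerated arousal, excitability, hypertonicity, quality of movement and stress abstinence). State what counts as a match and what is reported if no class matches. State how uncertain class membership is handled.
3. **Comparison.** Compare the atypical proportion by arm with the same logistic mixed model as H4 and H6, reporting the odds ratio and 95% CI. Name the logit link, because SAP 6.4.1 leaves the choice of link open.
4. **Status.** Treat any other data-driven class solution as exploratory, and declare the departure from the protocol. SAP 3.7 expected first-phase analysis from April 2024; if H8 has already been analysed, report when the class definition was fixed.

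Restoring the words Profile 5 alone would not be enough, because the protocol has no assignment algorithm. The cost is SAP wording and one arm-blind step. The downsides are that published parameters may be unavailable or may fit this pre-discharge cohort less well, and that a forced five-class fit may be unstable at about 300 infants.

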4.2 Protocol Violations/Deviations

Protocol violations (PV) and protocol deviation (PD) for pharmacy and non-pharmacy will be descriptively summarized in terms of infants per arm with any PV or PD and in terms of number of PV-PD per arm.

4.3 Analysis Datasets

The analyses for each outcome will be performed using an intention-to-treat (ITT) framework, defined as the inclusion of all infants randomized and consented into the study and analyzed according to the trial arm to which the infant was randomized to.

5 Trial Population

5.1 Screening population

Research personnel will screen medical records of pregnant mothers to identify mothers who use opioids, and screen charts of infants with known opioid exposure in utero and infants treated for NOWS in all areas of the hospital in which infants may receive care. After an infant is born from this population, they will be evaluated against the inclusion and exclusion criteria. Infants will be tracked to ensure eligibility by verifying the following: NOWS signs occurred, clinical team-initiated morphine or methadone treatment, and weaning after stabilization on an opioid dose has not started.

5.2 Withdrawal / Follow-up

Caregiver of infants withdrawn from the study will be given three options: 1. Discontinuation of study intervention with permission to continue study specific assessment and data collection, 2. Withdrawn with permission to continue data collection per protocol, or 3. Withdrawn with discontinuation of further data collection. If withdrawal status allows for continued data collection, then information about the number of days infants were treated for NOWS with opioids after withdrawal from the intervention will be collected.

5.3 Analysis Populations

The Full Analysis Set (FAS)¹ population will serve as the population for the analysis of efficacy data in this trial. The FAS population consists of all subjects randomly assigned to treatment who completed the treatment, this will include non-withdrawn infants as well as withdrawn infants with permission for continued data collection.

Survival analysis and safety analysis will utilize Intention-to-treat population, defined as the inclusion of all randomized participants. For the survival analysis, efficacy outcome for withdrawn infants with discontinuation of further data collected will be right censored.

5.4 Baseline Patient Characteristics

Infants and maternal baseline characteristics will be compared across treatment groups. Table 1 and 2, respectively. The table shells list out the characteristics that will be summarized. Other baseline characteristics may be investigated.

6 Statistical Analysis

6.1 Primary Outcome

[figure not shown]
6.1.1 Description of Primary Outcome Calculation

In the protocol, the primary outcome was defined as "The number of days of opioid treatment (used as primary treatment), including escalation, resumption, and spot treatment, from the first weaning dose to cessation of opioid". Additionally, the protocol specifies, "we will define days on a 24-hour basis, e.g., 18 hours will represent 0.75 days". For data collection on Form Weaning07, data was not collected at this detailed level of time and date for every dose. Instead, data was collected by steps with given time and dose of first dose in each step and total number of doses received by patient at this protocol step.

Considering the factors mentioned above, several aspects must be considered when determining the primary outcome. Initially, we identified time gaps that were at least two times the dosing intervals and excluded them from the calculation of the time spent on medication. It is crucial to note that during the first interval of these gaps, the infant was on treatment, which we will refer to as 'effective time on treatment.' These gaps are technically part of the duration of effect of the medication. Consequently, the time on the drug needs to be adjusted by one dose interval for each identified time gap.

Applying a similar rationale, an infant is considered "effectively on treatment" for one dose interval following the administration of the last study dose. Therefore, an additional dose interval is added to the cumulative total obtained thus far. To enhance clarity, the following example illustrates the methodology used in calculating the primary outcome for a non-withdrawn infant: The following figure represented a partial virtual timeline for an infant who was not withdrawn and was on Methadone treatment at an 8-hour interval. For this infant, the value of the primary outcome after looking at the dosing times through the first 96 hours is 96 hours or 4 days. In this instance, notice that we have a gap of 16 hours between the 5th and 6th dose, but the 5th dose was effective through hour 40 (32 + 8 hours). Next, the infant was on medication from 48-hour timepoint to 96-hour timepoint, this means 48 hours of treatment. So total time on treatment so far is 40 + 48, resulting in 88 hours. Finally, we add another 8 hours due to the effective treatment time after the 96-hour timepoint. This results in the final calculation of 96 hours on treatment.

Consider an infant with the following virtual timeline with dosing times given in hours since initial dose.

The time between 96 and 48 hours of treatemnt is 48 hours, so total so far is 40 + 48 = 88

Finally, add he last 8 hours due to effective treatment time after the 96 hour of treatment, 88 + 8 = 96 hours total.

Withdrawn Infants: One additional step is needed for infants who withdrew but have consented to continue data collection. On the Weaning12 form, section B, Q5b, we have a field where we can get "number of days infant was treated for NOWS with opioids after infant was withdrawn from the intervention". This number represents the days on treatment after withdrawal. As such, for infants who are withdrawn and give consent for continued data collection, we add the value recorded on Weaning 12, section B, Q5b to the value calculated above. Primary outcome for infants who withdrew with discontinuation of data collection will be censored and only included in the survival model.

Finally, per the protocol, "Infants will exit the study intervention without unblinding (remain in the trial) if they have not weaned off study drug by 35 days (inclusive of the 35th day) form the first weaning dose." To accommodate this, the primary outcome will be truncated at 35 days regardless of the study arm. The non-truncated data will be utilized in the planned survival sensitivity analyses using cutoff at 35 days as censoring indicator.

For full details on primary outcome calculation, please refer to PrimaryOutcomeCalculationWeaning.pdf

